## 1. LIST OF ABBREVIATIONS

**Table 1: List of Abbreviations**

Abbreviation	Term
ATC	Anatomical-Therapeutic-Chemical
BID	Twice daily dosing
CGI-I	Clinician Global Impression of Improvement
CGI-S	Clinician Global Impression of Severity
CI	Confidence interval
CSR	Clinical study report
CTCAE	Common terminology criteria for adverse events
ECG	Electrocardiogram
eCRF	Electronic case report form
FDA	Food and Drug Administration
LS	Least squares
MedDRA	Medical Dictionary for Regulatory Activities
MMRM	Mixed effect model of repeated measures
PCS	Potentially clinically significant
PGI-I	Patient Global Impression of Improvement
PGI-S	Patient Global Impression of Severity
PML	Progressive multifocal leukoencephalopathy
QPRO	Quality of Hair Patient Reported Outcome
SALT	Severity of Alopecia Tool
SAP	Statistical analysis plan
SPRO	Satisfaction of Hair Patient Reported Outcome
TEAE	Treatment-emergent adverse events
WHO	World Health Organization

## **2. PURPOSE OF THE ANALYSES**

This statistical analysis plan (SAP) provides a detailed description of the strategy and statistical methodology to be used for analysis of data from the CP543.2004 protocol, amendment 3.0, dated 09SEP2022.

This study will be ongoing at the time of the New Drug Application (NDA) submission. A database freeze will be implemented, and an abbreviated report will be included in support of the NDA submission. Ongoing safety data will also be submitted with the 120-day safety update report.

The purpose of this SAP is to describe the pre-specified statistical approaches to the analysis of study data prior to database freeze for the NDA submission and prior to database lock for the final report. In addition to the analyses pre-specified for the final clinical study report (CSR) upon study completion, this SAP will also describe the subset of analyses to be provided in the abbreviated report for the NDA submission.

This analysis plan is meant to supplement the study protocol. If differences occur between analyses described in the SAP and the current protocol, those found in this SAP will assume primacy. Any deviations from this plan will be described in the applicable study report.

### 3. PROTOCOL SUMMARY

This is a two part, double-blind, randomized, multicenter study to evaluate the regrowth of hair with CTP-543 and subsequent durability of that regrowth following dose reduction or drug discontinuation in adult patients with moderate to severe alopecia areata. Patients will be between 18 and 65 years of age and experiencing an episode of hair loss associated with alopecia areata lasting at least 6 months and not exceeding 10 years. Patients not currently being treated for alopecia areata or with other treatments that might affect hair regrowth or immune response must have at least 50% hair loss as measured by the Severity of Alopecia Tool (SALT) at Screening and Baseline.

The study is divided into 2 Parts:

**Part A:** Period 1 (Treatment Phase) and Period 2 (Dose Modification Phase)

**Part B:** Re-Treatment Phase

#### Part A

##### Period 1

Patients will be screened up to 28 days prior to initiation of study drug. Patients will provide appropriately-obtained informed consent prior to initiating any screening procedures. Patients meeting initial screening criteria will be eligible to continue to the Day 1 (Baseline) visit for review of eligibility and baseline assessments, including SALT assessment, physical examination, clinical laboratory assessments, electrocardiograms (ECGs) and vital signs. Patients meeting all inclusion criteria and none of the exclusion criteria are eligible to enter Part A, Period 1 of the study.

Part A, Period 1 is a double-blind Treatment Period where patients will be randomized to receive either 8 mg BID or 12 mg BID CTP-543 for 24-weeks. Randomization will be stratified by scalp hair loss into one of the following two categories: 1) Partial scalp hair loss (SALT  $\geq 50$  and  $<95$ ); 2) complete or near-complete scalp hair loss (SALT  $\geq 95$ ). Patients will take the first dose of study drug in the clinic on Day 1 and will be instructed to take study drug daily approximately every 12 hours for the duration of Period 1. Other baseline assessments for Part A, Period 1 will include Patient and Clinician Global Impression of disease Severity (CGI-S and PGI-S), and Patient Reported Outcome for Satisfaction (SPRO) and Hair Quality (QPRO). Blood samples for pharmacokinetic assessment will be taken periodically. At End of Treatment (EOT) for Part A, Period 1, treatment success (Responders) will be defined as patients from each dose group having an absolute SALT score of  $\leq 20$  at Week 24. These Responders will enter Part A, Period 2 of the study. Patients having an absolute SALT score  $> 20$  will be defined as a Non-Responder and will have the opportunity to continue receiving treatment in the Open-Label Extension study (CP543.5001) or they will complete treatment at Week 24 and return in 4 weeks for the Post-Treatment Safety Follow-up.

##### Period 2

In Part A, Period 2, patients will be re-randomized to receive either a lower dose of CTP-543 (4 mg BID for patients previously receiving 8 mg BID or 8 mg BID for patients previously

Concert Pharmaceuticals, Inc.  
Statistical Analysis Plan – CP543.2004

receiving the 12 mg BID) or placebo. Patients in Part A, Period 2 will stay on their assigned dose for a maximum of 24 weeks or until they meet the criteria for loss of regrowth maintenance (LOM), defined as an absolute SALT score  $>20$ . Any patient meeting the LOM criteria at any assessment timepoint during Part A, Period 2 will enter Part B of the study and return to their original CTP-543 treatment from Part A, Period 1 (8 mg BID or 12 mg BID). Patients not meeting the LOM criteria (e.g., their absolute SALT score  $\leq 20$ ) at the end of 24 weeks will have the opportunity to continue receiving treatment in the Open-Label Extension study (CP543.5001) or they will complete treatment at Week 24 and return in 4 weeks for the Post-Treatment Safety Follow-up. The study design is depicted in the Study Flow Chart of the Appendix (Section 15.1).

An interim analysis to support regulatory activities related to an upcoming CTP-543 New Drug Application (NDA) submission will be conducted. The focus of the interim analyses will be on safety data and will occur following completion of Part A, Period 1. Additionally, after Part A, Period 1 completion, a PK population analysis will be completed. The PK analysis will be conducted by an outside vendor. This analysis will be described in a separate analysis plan and a separate report will be generated.

The primary efficacy assessment will be conducted when all patients have completed Part A, Period 2. An analysis of safety data will also be conducted. This analysis will be included in the NDA submission as an abbreviated report. Site personnel and patients will remain blinded to individual patient study treatments.

## Part B

Any patient from Part A, Period 2 meeting the LOM criteria (SALT  $> 20$ ) will enter into Part B of the study and return to their original 8 mg BID or 12 mg BID dose assigned in Part A, Period 1. Patients will stay on their assigned dose for 24 weeks regardless of whether they meet the criteria for Restoration of Regrowth (ROR) or not. ROR is defined as the patient's attainment of an absolute SALT score of  $\leq 20$ . Assessment of treatment response using SALT for efficacy will occur monthly during the 24-week period. Patients will have the opportunity to continue receiving treatment in the Open-Label Extension study (CP543.5001) or they will complete treatment at Week 24 and return in 4 weeks for the Post-Treatment Safety Follow-up.

Patient safety will be monitored throughout the trial by the Investigator and supported by regular review by the Medical Monitor. Chemistry and hematology laboratory values will be assessed under fasted conditions bi-weekly for the first month of the treatment period (Part A, Period 1 and Part B), followed by every 4 weeks through the remainder of the study (all Parts). Lipid levels will be assessed every 4 weeks throughout the study. In light of the COVID-19 pandemic, challenges in the conduct of study visits may arise from quarantines, site closures, and/or travel limitations. To ensure the safety of trial participants and to minimize risk to trial integrity, alternative methods for drug dispensation and assessments, including telemedicine visits and clinical laboratory blood draws at a local laboratory or via a Home Health Care agency, may be offered for those trial participants who may no longer have access to the investigational site. Significant cytopenias or other hematologic abnormalities will be managed by severity through dose interruption or discontinuation, and signs and symptoms of infection will be closely monitored and treated promptly. Patients who experience intolerable symptoms during treatment may discontinue treatment at the judgement of the Investigator, but will be followed for safety

Concert Pharmaceuticals, Inc.  
Statistical Analysis Plan – CP543.2004

and efficacy assessments for the remainder of the study unless they withdraw consent. Patients may withdraw consent at any time.

#### 4. GENERAL ANALYSIS AND REPORTING CONVENTIONS

The following is a list of general analysis and reporting conventions to be applied to this study, unless otherwise specified. Departures from these general policies will be described, if applicable, in the appropriate sections of this SAP. When this situation occurs, the rules set forth in the specific section take precedence over the general policies.

All data displays (tables, listings, and figures) will have a header showing the sponsor company name, protocol number, page number, and display status (i.e. “DRAFT” or “FINAL”), as well as a footer indicating file name and run date/time. Summary tables and data listings will be summarized by treatment group for efficacy and exposure, and by treatment group and overall otherwise. All data for analysis may be listed by-patient.

Specifically, for each Part and Period of the study, the summary table layout will be as follows:

For Part A, Period 1 tables:

Treatment Phase		
CTP-543 8 mg BID	CTP-543 12 mg BID	Total

For Part A, Period 2 tables:

Dose Reduction		Drug Discontinuation		Total
CTP-543 8 mg BID to 4 mg BID	CTP-543 12 mg BID to 8 mg BID	CTP-543 8 mg BID to Placebo	CTP-543 12 mg BID to Placebo	

For Part B tables:

Dose Reduction		Drug Discontinuation		Total
CTP-543 8 mg BID to 4mg BID to 8 mg BID	CTP-543 12 mg BID to 8 mg BID to 12 mg BID	CTP-543 8mg BID to Placebo to 8 mg BID	CTP-543 12 mg BID to Placebo to 12 mg BID	

Note that for all efficacy and exposure tables, the total column will not be displayed.

Categorical variables will be summarized using counts (n) and percentages (%) and will be presented in the form “n (xx.x).” If a count is 0, no percentage will be shown. If a percentage is 100%, 100 will be shown. To ensure completeness, summaries for categorical variables will include all categories, even if no patients had a response in a particular category. Unless otherwise specified, the denominator for each percentage will be based on the number of patients in the population being summarized (header n). Percentages will be rounded to one decimal place.

Continuous variables will be summarized using mean, standard deviation, minimum, maximum, median, and number of patients. The minimum and maximum will be the same precision as the

Concert Pharmaceuticals, Inc.  
Statistical Analysis Plan – CP543.2004

original collected data. The mean and median will be reported to an additional level of precision than the original observations, and the standard deviation will be reported to two additional levels of precision than the original observations. The precision for some original collected data and derived variables are longer than required for clinical interpretation (eg, >15 decimals). In these situations, the number of decimal places will be determined by the table of precision included as an attachment.

All efficacy summaries are descriptive with no statistical hypothesis testing. Confidence intervals and estimated treatment differences will be rounded to one additional decimal place from the original data, or a maximum of two decimal places. Standard error will be reported to an additional level of precision. Results which cannot be determined will be displayed as “NA”, “NE”, or similar.

Treatment start date for each part and period will be defined as the date of randomization or re-randomization for the respective part or period. If the treatment start date for Part A Period 2 is equal to the treatment end date for Part A Period 1 as collected on the eCRF, it will be assumed that the treatment day is associated with Part A Period 2. One day will be subtracted from the treatment end date for Part A Period 1. Similarly, if the treatment start date for Part B is equal to the treatment end date for Part A Period 2, it will be assumed that the treatment day is associated with Part B. One day will be subtracted from the treatment end date for Part A Period 2.

Date of last dose is collected on the *Treatment Discontinuation/Completion* eCRF page for each part/period. For patients with missing or partial date of last dose, or for patients who are ongoing at the time of the NDA submission, the date of last dose (ie, treatment end date) will be imputed. Date of last dose will be imputed as follows:

- For entirely missing dates for patients who are not ongoing or for partial dates where the month and day are missing, date of last dose will be imputed as the last visit date that is not a follow-up visit within a period or part.
- For partial dates where only the day is missing, the day will be imputed as the last day of the month. If this imputed date is after the treatment start date of the next part or period, or the study discontinuation date of that part or period, the day will be imputed to one day before the treatment start date of the next part or period.
- For patients who are ongoing, date of last dose will be imputed as the data cut date.

Summary tables and data listings:

- No preliminary rounding will be performed; rounding will only occur after analysis. Note that for the clinical purposes of moving patients through parts and periods, SALT scores were rounded to the nearest integer prior to determining the SALT  $\leq 20$  criterion.
- Data from patients excluded from an analysis population will be presented in the data listings but will not be included in the calculation of summary statistics, where applicable.

Concert Pharmaceuticals, Inc.  
Statistical Analysis Plan – CP543.2004

- Data from each patient will be separated by a blank line. Within a data listing, if a descriptive item appears line after line (e.g., repetition of a patient number, date, visit, etc.), only the first occurrence will be displayed (e.g., in Listing of Vital Signs, patient number, date and visit will only be displayed on first row when presenting all parameters collected at same visit). Repetition of actual results or outcomes (e.g., adverse events, lab results, vital sign values, etc.) will not be collapsed.
- Data listings will be sorted by treatment, patient, and date and/or time of assessment, as applicable. Data listings may be separated by study part.
- There will be 3 baselines in this study, defined as follows:
  - Part A Period 1 baseline is the last observation obtained on or before the day of dosing of study drug in Part A Period 1.
  - Part A Period 2 baseline is the last observation obtained on or before the day of dosing of study drug in Part A Period 2.
  - Part B baseline is the last observation obtained on or before the day of dosing of study drug in Part B.
- Unless otherwise noted, values reported as greater than or less than some quantifiable limit (e.g., “< 2.0”) will be summarized as using the numeric equivalent in summary tables and figures (e.g. “<2.0” will be analyzed as 2.0). The reported value will be used in listings.

Mock tables and data listings will be provided as attachments to this analysis plan. Minor changes to the mocks after formal SAP approval will not necessitate re-approval unless changes to the text of the SAP are required.

All statistical deliverables will be produced, validated, and reviewed for accuracy/consistency in accordance with [REDACTED] standard operating procedures and the processes described in the statistical validation plan.

SAS® (SAS Institute, Cary, North Carolina) statistical software, version 9.4 or later, will be used for all analyses. Adverse Events and Medical History will be coded in Medical Dictionary for Regulatory Activities (MedDRA) Version 23.1 or later. Concomitant medications will be coded in World Health Organization (WHO) Drug Version 2020-SEP or later, and Anatomical-Therapeutic-Chemical (ATC) classification and preferred term will be used for summaries.

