Primary Efficacy Analysis Part B (Re-Treatment Phase)

The primary efficacy analysis for Part B is the proportion of patients by dose group achieving ROR, defined as an absolute SALT score of \leq 20 at Week 24 of re-treatment.

Secondary Endpoints for Part B

- Percentage of patients achieving the ROR criteria at Weeks 4, 8, 12, 16, and 20
- Relative change in SALT scores from Part B Baseline at Weeks 4, 8, 12, 16, 20, and 24

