13.4. Analyses

For each study phase, data will be summarized by dosing group (8 mg BID versus 12 mg BID). All data for analysis will be listed by patient.

Continuous measures will be summarized descriptively (mean, standard deviation, median, minimum value, and maximum value) and categorical measures will be presented as number and percentage.

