### Part B:

For Part B of the study, the primary efficacy endpoint is the percentage of patients by dose group achieving ROR, defined as an absolute SALT score of  $\leq 20$  at Week 24 of re-treatment. The following treatment sequences will be compared:

- Dose reduction in Period 2
  - 12 mg BID reduced to 8 mg BID increased to 12 mg BID
  - 8 mg BID reduced to 4 mg BID increased to 8 mg BID

- Drug discontinuation in Period 2
  - 12 mg BID to placebo to 12 mg BID
  - 8 mg BID to placebo to 8 mg BID

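### The SAP plans no display of the protocol's Part B primary result, restoration of regrowth by re-treatment dose (8 mg BID, 12 mg BID), and does not record the move to four treatment sequences as a change

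*SAP*

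**What the plan says.** **Protocol.** Section 13.2.1 states: "The primary efficacy analysis for Part B is the proportion of patients by dose group achieving ROR", with ROR being SALT of 20 or less at Week 24 of re-treatment. Section 13.4 gives the grouping: "For each study phase, data will be summarized by dosing group (8 mg BID versus 12 mg BID". Section 8.3 treats a dose group in Part B as everyone who lost maintenance after either Period 2 arm and went back to the same starting dose. Section 13.1 likewise places a reduction arm and a discontinuation arm inside each dose group.

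**SAP.** Section 8.2, Part B, says "the primary efficacy endpoint is the percentage of patients by dose group achieving ROR" and continues "The following treatment sequences will be compared", followed by four sequences. Section 8.2.2 reports counts, percentages and 95% intervals by treatment group. Section 4 sets the Part B columns: the first is "CTP-543 8 mg BID to 4mg BID to 8 mg BID", the others are 12-8-12, 8-placebo-8 and 12-placebo-12, and then comes a Total. On the Total, Section 4 says "Summary tables and data listings will be summarized by treatment group for efficacy and exposure, and by treatment group and overall otherwise" and "Note that for all efficacy and exposure tables, the total column will not be displayed". In Section 15.4, Table 14.2.1.2 is the only Part B primary table, and no table or figure title there mentions pooling by dose. Section 13 lists smaller departures from the protocol, such as an added Week 4 summary, but not this one. Section 2 lets the SAP prevail where the two documents differ.

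**The concern.** Under the protocol, the primary Part B result is two proportions, one per re-treatment dose. Under the SAP's layout it becomes four, one per sequence. A programmer who follows SAP 4 and 8.2.2 would fill Table 14.2.1.2 with the four and have no instruction to produce the two.

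The secondary objective asks what re-treatment at the original dose achieves. Part B holds only patients with LOM, from Period 2 arms expected to number about 25 each, so each sequence can be very small. It will be smallest where dose reduction preserved hair best. The study would then report only its least precise Part B figures, while the estimate that the protocol named is left for readers to assemble.

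**Working it through.** **1. The plan's own figure.** Protocol 13.1 expects about 50 Responders per dose group, randomized 1:1. 50 / 2 = 25 per Period 2 arm, as stated. Period 1 also adds up: 170 + 130 = 300. A Part B sequence can therefore hold at most about 25 patients, and a dose group at most about 50. There is no power calculation to reproduce.

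**2. Which planned column gives the protocol's estimate?**

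| Column in the SAP 4 Part B layout | Patients | Is it a dose group? |
|---|---|---|
| 8-4-8 | 8 mg, after reduction | Part of one |
| 8-placebo-8 | 8 mg, after placebo | Part of one |
| 12-8-12 | 12 mg, after reduction | Part of one |
| 12-placebo-12 | 12 mg, after placebo | Part of one |
| Total (not shown for efficacy or exposure) | Both doses | No, it mixes two |

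None does.

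**3. Can it be recovered?** For the primary endpoint, yes. With x responders among n patients in each sequence,

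ROR(8 mg) = (x[8-4-8] + x[8-placebo-8]) / (n[8-4-8] + n[8-placebo-8]),

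and likewise for 12 mg. With invented counts of 3/5 and 13/20, this is 16/25 = 64.0%, and the SAP's interval is 43.2% to 84.8%. Medians of SALT change cannot be rebuilt from sequence summaries in this way; they need the patient-level data.

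**4. What does the split do to precision?** I used the SAP 8.2.2 interval, a Wald interval with continuity correction:

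half-width = 1.96 × √(p(1 − p)/n) + 1/(2n).

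The documents give no LOM or ROR rates, so these are assumptions: 25 per Period 2 arm, p = 0.60, and three LOM scenarios (reduction / placebo). The n are expected values, hence the fractions.

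| LOM | n: reduction, placebo, pooled | Half-width in points: reduction, placebo, pooled |
|---|---|---|
| 20% / 70% | 5, 17.5, 22.5 | 52.9, 25.8, 22.5 |
| 30% / 70% | 7.5, 17.5, 25 | 41.7, 25.8, 21.2 |
| 40% / 80% | 10, 20, 30 | 35.4, 24.0, 19.2 |

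Worked line for n = 25: 1.96 × √(0.24/25) + 1/50 = 0.192 + 0.020 = 0.212. For n = 7.5: 1.96 × √(0.24/7.5) + 1/15 = 0.351 + 0.067 = 0.417.

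At the upper bound, where every Period 2 patient has LOM, n is 25 per sequence and 50 per dose. With ROR at 50%, the half-width falls from 21.6 to 14.9 points.

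**The case against.** **The SAP has not dropped the endpoint.** Section 8.2 still says by dose group, and Section 4 provides that "the rules set forth in the specific section take precedence over the general policies". This stands in part. It means that a reader who infers that the dose-group result will never be produced goes too far. But the specific section also lists the four sequences, so it does not clearly override the layout. Mock tables could settle the matter; Section 4 promises them as attachments, but Section 16 lists none.

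**The result can be derived.** True for the proportion and its interval, as shown. That limits the harm to reporting. It is still reasonable to expect a primary estimate to be programmed, validated and displayed.

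**The suppressed Total.** A reader might infer that dropping the Total removes the primary result, or that no Part B table has an overall column. Neither is supported. The Total is dropped only from efficacy and exposure tables, and it would combine 8 mg with 12 mg in any case.

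**Adverse events.** A reader might infer that Part B adverse events are never shown by the dose taken. That is wrong: each sequence column contains a single Part B dose. Only the sum over two columns is absent.

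**Protocol 13.4 is loose.** Applied literally to Period 2, it would merge arms that the co-primary analyses keep apart, and the protocol leaves further statistical detail to the SAP. Fair, but Sections 8.3 and 13.1 support the same meaning of dose group without it. For the Part B secondaries the protocol is less firm: only the synopsis says by dose group.

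**The sequences are informative.** Also true. The secondary objective refers to re-treatment after reduction or discontinuation, and a pooled figure is a mixture whose weights depend on the LOM rate in each arm. This is a reason to keep the sequences, not to omit the dose groups.

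**Conclusion.** The point holds as a gap in planned reporting. The protocol's Part B primary estimate has no planned display, SAP 8.2 is internally inconsistent about the unit of summary, and SAP 13 does not acknowledge the difference. No data are lost, and no test is affected, because the study is descriptive.

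Under the assumed rates, pooling by dose gives half-widths of about 19 to 23 points, against 35 to 53 points for the reduction sequences and 24 to 26 points for the placebo sequences. These figures illustrate the scale and predict nothing. At the smallest n the Wald interval runs past 100% (60 + 52.9 points), so those widths also reflect the interval method. A narrower pooled interval follows from any pooling and does not by itself make the sequence display an error. The case for change rests on the protocol having named the dose-group estimate as primary.

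**What to change.** In SAP 8.2, state that the Part B primary endpoint is summarized for each re-treatment dose, and that the four sequences are a descriptive breakdown. In SAP 4, add two columns to the Part B efficacy layout, 'All re-treated 8 mg BID' and 'All re-treated 12 mg BID'. Show n, percentage and 95% interval in these columns of Table 14.2.1.2 as the primary display. Add the same columns to Table 14.2.2.3 (ROR by visit) and Table 14.2.2.6.6 (SALT change from Part B baseline) for the secondaries. In the Part B safety tables they are an optional convenience.

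If the sponsor means the sequences to replace the dose groups, SAP 13 should say so and give the reason.

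The cost is a few lines of SAP text and two columns in existing tables, with no new data. SAP 15.4 does not mark the Part B efficacy tables for the abbreviated report, so the change affects only the final study report.
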